3.5. Pharmacokinetic Measures and Time Points

Pharmacokinetics will not be assessed in this study.

3.6. Exploratory Efficacy Measures and Time Points

The exploratory efficacy measures and time points are:

- biological markers of inflammation and asthma:
 - IgE
 - DPP4
 - 25-hydroxy vitamin D
 - eotaxin-1, -2, and -3
 - TARC
 - MCP-1 and MCP-4
 - ILC2
- lung function variables:
 - FVC
 - PEFR
 - FEF_{25%-75%}
- the global uptake of FDG in the lymph nodes and bone marrow as measured by the PET/CT imaging parameters indicated for the primary efficacy variable
- for those patients that can produce sputum, to demonstrate a correlation between reductions in inflammation by reslizumab with a reduction in sputum eosinophils

All variables will be measured at 1 (biomarkers only) or 2 baseline visits and at weeks 2, 4, and 6 post-randomization.

3.7. Randomization and Blinding

This is a randomized, double-blind, placebo-controlled study. After the 2 baseline PET/CT scans and successful completion of all requirements (Part 1), patients will be randomly assigned 1:1 in a double-blind fashion to receive either placebo or iv 3.0 mg/kg reslizumab.

In order to maintain the blind, each patient will be assigned a unique identifier number and all reference to the patient will be by using this identifier.

Patients will be randomly assigned to treatment groups by means of a computer-generated randomization list. The specifications for randomization will be under the responsibility and

oversight of Teva Global Statistics. The output of the randomization process will be a patient randomization list.

The sponsor's clinical personnel involved in the study will be blinded to the study drug identity until the database is locked for analysis and the treatment assignment is revealed, with the exception of the bioanalytical group who will not be blinded to facilitate ADA sample analysis and an un-blinded person who will be responsible for randomization assignment. Additionally, in order to maintain the study blind, blood and sputum eosinophil levels assessed after study drug administration will not be available to investigators, their blinded staff, the sponsor, and blinded members of the clinical research organization. There will be un-blinded data management, un-blinded site staff, and an un-blinded CRA who will not sit on the study team and be responsible for un-blinded eosinophil data.

3.8. Maintenance of Randomization and Blinding

3.8.1. Maintenance of Randomization

Patient randomization codes will be maintained in a secure location at the service provider contracted to generate the codes. At the time of analysis (after the end of study), after receiving unblinding request from Teva statistician, the service provider will provide the unblinded treatment assignment according to the processes defined in the relevant Standard Operating Procedure (SOP).

3.8.2. Blinding/Unblinding

For information about personnel who may be aware of treatment assignments, see Section [3.7](#). These individuals will not be involved in conduct of any study procedures or assessment of any adverse events.

An envelope containing individual sealed envelopes that correspond to each study drug package will be provided to the investigational center. The envelopes will contain the randomization number and the name and dose (if applicable) of the study drug for each patient. In case of a serious adverse event, pregnancy, or in cases when knowledge of the study drug assignment is needed to make treatment decisions, the investigator may open the patient's envelope and unblind the patient's drug assignment as deemed necessary, mainly in emergency situations. If possible, the sponsor should be notified of the event before breaking of the code. If this is not possible, the sponsor should be notified immediately afterwards and the patient's drug code assignment should not be revealed. All envelopes must be returned to the sponsor at the completion of the study. Breaking of the treatment code can always be performed by the investigational center without prior approval by the sponsor.

When a blind is broken, the patient will be withdrawn from the study and the event will be recorded on the case report form (CRF). The circumstances leading to the breaking of the code should be fully documented in the investigator's study files and in the patient's source documentation. Treatment assignment should not be recorded in any study documents or source document.

In blinded studies, for an adverse event defined as a suspected unexpected serious adverse reaction (SUSAR) (ie, reasonable possibility; see Section [7.1.4](#)), Global Patient Safety and Pharmacovigilance may independently request that the treatment code be broken (on a

case-by-case basis) to comply with regulatory requirements. The report will be provided in an unblinded manner for regulatory submission. If this occurs, blinding will be maintained for the investigator and for other personnel involved in the conduct of the study, and analysis and reporting of the data.

3.8.3. Data Monitoring Committee

A Data Monitoring Committee will not be used during this study.

3.9. Drugs Used in the Study

A description of administration procedures is given in Section [5.1](#).

Additional details may be found also be found in the current US PI for reslizumab ([CINQAIR 2016](#)) and for FDG 18 ([FDG 2014](#)).

3.9.1. Investigational Product

Reslizumab will be provided as a sterile solution for infusion presented as 100 mg (10 mL) per vial, formulated at 10 mg/mL in 20 mM sodium acetate, 7% sucrose, pH 5.5 buffer.

The contents of the label will be in accordance with all applicable local regulatory requirements.

A more detailed description of administration procedures is given in Section [5.1](#).

3.9.2. Placebo

Placebo will be provided as a sterile solution of 20 mM sodium acetate, 7% sucrose, pH 5.5 buffer.

A more detailed description of administration procedures is given in Section [5.1](#).

3.9.3. Fludeoxyglucose F 18

Fludeoxyglucose F 18 injection will be provided as a ready to use isotonic, sterile, pyrogen free, clear, colorless citrate buffered solution. Each mL will contain between 0.740 to 7.40 gigabecquerel (20.0 to 200 millicurie [mCi]) of 2-deoxy-2-[¹⁸F]fluoro-D glucose at the end of synthesis (EOS), 4.5 mg of sodium chloride and 7.2 mg of citrate ions. The pH of the solution will be between 5.5 and 7.5. The solution will be packaged in a multiple-dose glass vial and will not contain any preservative.

A more detailed description of administration procedures is given in Section [5.1](#).

3.10. Drug Supply and Accountability

3.10.1. Drug Storage and Security

3.10.1.1. Reslizumab and Placebo

Reslizumab and matching placebo must be stored in a refrigerator at controlled temperature (2°C to 8°C) and should not be frozen and should be protected from light. Reslizumab and placebo supplies must be kept in a secure area (eg, locked refrigerator). The site should have a process for monitoring the storage temperature of unused study drug.

3.10.1.2. Fludeoxyglucose F 18

Receipt, transfer, handling, possession, or use of FDG is subject to the radioactive material regulations and licensing requirements of the US Nuclear Regulatory Commission, Agreement States or Licensing States as appropriate.

The FDG vial must be stored upright in a lead shielded container at 25°C (77°F); excursions permitted to 15°C to 30°C (59°F to 86°F).

Store and dispose of FDG in accordance with the regulations and a general license, or its equivalent, of an Agreement State or a Licensing State. The expiration date and time are provided on the container label. Use FDG within 12 hours from the EOS time.

3.10.2. Drug Accountability

Each study drug shipment will include a packing slip listing the contents of the shipment, drug return instructions, and any applicable forms.

The investigator is responsible for ensuring that deliveries of study drug and other study materials from the sponsor are correctly received, recorded, handled, and stored safely and properly in accordance with the CFR or national and local regulations, and used in accordance with this protocol.

A record of study drug accountability (ie, study drug and other materials received, used, retained, returned, or destroyed) must be prepared and signed by the principal investigator or designee, with an account given for any discrepancies. Empty, partially used, and unused study drug will be disposed of or returned to the sponsor or designee.

3.11. Duration of Patient Participation and Justification

This study will consist of Part 1, a 21-day PET/CT screening period, and Part 2 (only patients with asthma), a 6 week double blind treatment/assessment period followed by a 7-day follow up period. See Section 12.4 for the definition of the end of study.

3.12. Stopping Rules and Discontinuation Criteria

Other than in the event a participant becomes pregnant, there are no formal rules for early termination of this study. During the conduct of the study, serious adverse events will be reviewed by Teva in an ongoing basis (see Section 7.1.5) as they are reported to Teva by the investigational center to identify safety concerns.

The study may be terminated by the sponsor for reasons including, but not limited to, a safety concern.

Termination of patient participation is required in Part 2 in the event of an asthma exacerbation. Should this happen, additional patients will be enrolled until 10 patients (including at least 4 female patients) have completed all 3 post-reslizumab/placebo PET/CT scans.

A patient may discontinue participation in the study at any time for any reason (eg, lack of efficacy, withdrawal of consent, and adverse event); every effort should be undertaken to find out the reason for discontinuation. The investigator or sponsor can withdraw a patient from the

study at any time for any reason (eg, protocol violation or deviation as defined in Section [11.1.2](#), noncompliance, or adverse event).

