sLV and lung sSUV mean from each slice. The lung volume (LV) will be calculated by adding all the sLV from slices passing through the lung, and the GLG will be determined by adding all the sLG from slices passing through the lung. Finally, the lung SUV mean will be calculated by dividing the GLG by the LV. Applying this methodology to different tissues or regions of the lungs will allow us to determine average and global SUV measures for the following tissues: whole lung parenchyma, right and left lung parenchyma, trachea, bronchi, and right and left bronchi. These regions will be delineated in the CT images by using the image segmentation techniques. These tissue volumes will be registered with the PET images as outlined below for the estimation of SUVs within these regions. Similar methodology will be applied to the lymph nodes and bone marrow.

[figure not shown]
The assessments and procedures performed during each study visit are detailed in [Table 2](#) and [Section 3.14](#). If a patient elects to withdraw (or is discontinued from treatment by the investigator), every attempt will be made to continue the assessments subsequent to his/her withdrawal from the study (see [Section 4.4](#)).

Schemas presenting the walk-through of the study are shown in [Figure 1](#), [Figure 2](#), and [Figure 3](#).

[figure not shown]
Figure 1: Health Control Subjects-Study Flow

AE=adverse event; β-HCG=beta-human chorionic gonadotropin; Bp1=baseline Part 1; Comp=complete; Con=concomitant; CT=computerized tomography; d=day; ECG=electrocardiography; EOS=eosinophils; FEV₁=forced expiratory volume in 1 second; GLG=global lung glycolysis; H=height; Hx=history; IC=informed consent; I/E=inclusion/exclusion; Labs=laboratory samples; Med=medical; meds=medications; P/E=physical exam; [REDACTED]; PET=positron emission tomography; pts=patients; [REDACTED]; s=serum; Sm=smoking; u=urine analysis; V=visit; W=weight

Figure 2: Patients with Asthma-Study Flow: Part 1

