3.14. Study Procedures and Assessments

Study procedures and assessments with their time points are summarized in [Table 2](#). Detailed by-visit information is provided starting with Section [3.14.1](#). Detailed descriptions of each assessment are provided in Section [6](#) (efficacy assessments), Section [7](#) (safety assessments), and Section [8](#) (other assessments).

Table 2: Study Procedures and Assessments

Study period	Part 1			Part 2				Follow-up
Visit number	V1 ^a	V2	V3	V4	V5	V6	V7	V8
Allowed time windows	Up to -21 days	0 days	±3 day(s)	Within 3 days of V3	±3 day(s)	±3 day(s)	±3 day(s)	Up to +7 days
Procedures and assessments	Screening [REDACTED]	Baseline (day 1) [REDACTED]	W1 (day 8) [REDACTED]	Baseline (day 1) [REDACTED]	W2 (day 15 from V4) [REDACTED]	W4 (day 29 from V4) [REDACTED]	W6 (day 43 from V4)/early termination [REDACTED]	W7
Informed consent	X	X						
Medical history	X							
Smoking history	X							
Prior medication and treatment history	X							
Complete physical examination ^b	X						A	
Brief physical examination ^b				A	A	A		
Vital signs measurement ^{bc}	X			A	A	A	A	
Inclusion and exclusion criteria	X	X						
Clinical chemistry ^{bd}	X			A			A	
Urine/serum β HCG test for women of child bearing potential ^{be}	X	X	X	A	A	A	A	
Hematology (eosinophils) ^f	X			A	A	A	A	
Sputum sampling for eosinophils ^g	X			A	A	A	A	
Urinalysis ^h	X	X	X		A	A	A	
PET/CT scan [REDACTED] ⁱ		X	X		A	A	A	
ACQ-6 for entry criterion	A							
Electrocardiography ^b	X							
Spirometry	X			A	A	A	A	

Clinical Study Protocol

Placebo-Controlled Study–Asthma with Eosinophilia
Study CEP38072-AS-40105

Study period	Part 1			Part 2				Follow-up
Visit number	V1 ^a	V2	V3	V4	V5	V6	V7	V8
Allowed time windows	Up to -21 days	0 days	±3 day(s)	Within 3 days of V3	±3 day(s)	±3 day(s)	±3 day(s)	Up to +7 days
Procedures and assessments	Screening [REDACTED]	Baseline (day 1) [REDACTED]	W1 (day 8) [REDACTED]	Baseline (day 1) [REDACTED]	W2 (day 15 from V4) [REDACTED]	W4 (day 29 from V4) [REDACTED]	W6 (day 43 from V4)/early termination [REDACTED]	W7
ADA ^{bj}				A	A		A	
Blood collection for biomarker analysis ^b				A	A	A	A	
AQLQ				A	A	A	A	
Randomization				A ^k				
Study drug infusion				A				
Adverse event inquiry	X	X	X	A	A	A	A	A
Concomitant medication inquiry	X	X	X	A	A	A	A	A

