4.3. Justification for Key Inclusion and Exclusion Criteria

4.4. Withdrawal Criteria and Procedures

In accordance with the Declaration of Helsinki, each patient is free to withdraw from the study at any time. The investigator also has the right to withdraw a patient from the study in the event of intercurrent illness, adverse events, pregnancy (see Section 7.2), or other reasons concerning the health or well-being of the patient, or in the event of lack of cooperation. In addition, a patient may be withdrawn from the study as described in Sections 3.8, 3.12, 3.14.4, 5.4, and 7.1.8.

Should a patient decide to withdraw after administration of study drug(s), or should the investigator decide to withdraw the patient, all efforts will be made to complete and report all observations up to the time of withdrawal. A complete final evaluation at the time of the patient's withdrawal should be made and an explanation given as to why the patient is withdrawing or being withdrawn from the study.

The reason for and date of withdrawal from the study must be recorded on the source documentation and transcribed to the CRF. If a patient withdraws consent, every attempt will be made to determine the reason. If the reason for withdrawal is an adverse event or a clinically significant abnormal laboratory test result, monitoring will be continued at the discretion of the investigator (eg, until the event has resolved or stabilized, until the patient is referred to the care of a health care professional, or until a determination of a cause unrelated to the study drug or study procedure is made). The specific event or test result must be recorded on the source documentation and transcribed to the CRF.

All assessments should be performed according to the protocol.

A patient who is has been identified as a potential participant but does not complete the screening period may be replaced with another eligible patient to ensure that at least 10 asthma patients (with at least 4 females) are evaluable for post-reslizumab PET/CT.

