9.3. Data Handling Conventions

For all variables, only the observed data from the patients will be used in the statistical analyses, ie, there is no plan to estimate missing data, unless otherwise specified.

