## INTRODUCTION

This Statistical Analysis Plan describes the planned analysis and reporting for Teva Branded Pharmaceutical Products R&D, Inc study CEP38072-AS-40105, (Distribution of Eosinophils in Asthma after Reslizumab (DEAR). A 7-week, Placebo-Controlled, Double-Blinded, Parallel-Group, Imaging Study Using Positron Emission Tomography/Computed Tomography (PET/CT) to Characterize the Effect of Intravenous Reslizumab on Airway Inflammation in Patients with Eosinophilic Asthma), and was written in accordance with SOP GBP\_RD\_702 (Statistical Analysis Plan).

The reader of this Statistical Analysis Plan is encouraged to read the study protocol for details on the conduct of this study, the operational aspects and times of clinical assessments, and the timing for completing the participation of a patient in this study.

The SAP is intended to be in agreement with the protocol, especially with regards to the primary and all secondary endpoints and their respective analyses. However, the SAP may contain more details regarding these particular points of interest, or other types of analyses (e.g. other endpoints). When differences exist in descriptions or explanations provided in the study protocol and this Statistical Analysis Plan, the Statistical Analysis Plan prevails; the differences will be explained in the Clinical Study Report.

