### **4.3. Handling Withdrawals and Missing Data**

Overall mean scores for AQLQ (Asthma Quality of Life Questionnaire at each visit of Part 2) and ACQ-6 (6-item Asthma Control Questionnaire for entry criterion at Screening for patients with asthma only) will be calculated for patients who answer all the questions. For the item analysis, the mean of the score by domain will be computed if all questions of the domain are answered.

For the AQLQ questionnaire, if a lot of missing data are observed, it will be dealt with by imputing mean values where more than half of the responses to a subscale will be present, as sensitive analysis (Apfelbacher et al. 2012).

For all other variables, only the observed data from the evaluable patients/subjects up to study completion or study withdrawal will be used in the statistical analyses, i.e., there is no plan to impute missing data for other variables.

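### Early-termination PET/CT scans share the week-6 visit label with no study-day rule, so they can enter the week-6 GLG mean on any day and be missing from week 4; SAP 4.3 also leaves unclear whether post-withdrawal scans count

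*Protocol*

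**What the plan says.** **Termination and replacement.** Protocol 3.12: "Termination of patient participation is required in Part 2 in the event of an asthma exacerbation". In that event "additional patients will be enrolled until 10 patients (including at least 4 female patients) have completed all 3 post-reslizumab/placebo PET/CT scans". The target is 10 completers overall; no number per arm is given.

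**Visit label.** The V7 column of Protocol Table 2 (section 3.14) is headed "W6 (day 43 from V4)/early termination" and includes a PET/CT scan. SAP Table 1 has the same shared column with a scan, at day 42. SAP 6.2.1 maps weeks 2, 4 and 6 to V5, V6 and V7. SAP 4.4 summarises by visit, taking the last non-missing value whether scheduled or not. It has no study-day analysis window and no rule for early-termination assessments.

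**Collection after withdrawal.** Protocol 3.1 says "every attempt will be made to continue the assessments subsequent to his/her withdrawal from the study", and SAP 2.1 repeats this. Protocol 4.4 is narrower: "all efforts will be made to complete and report all observations up to the time of withdrawal", plus a complete final evaluation. Protocol 3.14.4 places that evaluation at an end-of-treatment visit or as soon as possible afterwards.

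**Data used.** Protocol 9.3: "only the observed data from the patients will be used in the statistical analyses". SAP 4.3, for variables other than the questionnaires: "only the observed data from the evaluable patients/subjects up to study completion or study withdrawal will be used in the statistical analyses". Each sentence goes on to explain itself as meaning that missing data will not be filled in. On precedence, the SAP Introduction states: "When differences exist in descriptions or explanations provided in the study protocol and this Statistical Analysis Plan, the Statistical Analysis Plan prevails".

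**The concern.** The main Part 2 result is the difference between arms in mean GLG change at week 4, with 5 patients planned per arm. Every value in that mean needs a defined visit and a clear rule on whether it counts. For patients who exacerbate, the plan has neither.

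These losses are related to outcome and may differ by arm. Protocol 1.3.2.2 reports fewer exacerbations on reslizumab, and asthma adverse events in 23% of reslizumab patients against 40% on placebo in the pooled studies. Patients with a week-4 value may therefore not represent the groups as randomised. The planned n per visit and withdrawal reasons will show that someone is missing. They will not show that an existing scan was placed in the wrong week or left out.

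**Working it through.** The plan has no figure to reproduce: the 10 patients are set on clinical and practical grounds, with no effect size, SD, alpha or power. The check is a trace of the rules, with arithmetic for scale only.

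**1. Which days count as week 2, 4 or 6?** The nominal study days in Protocol Table 2 are 15, 29 and 43, each ±3. The protocol gives three readings of when the scan falls:

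| Reading | Week 2 | Week 4 | Week 6 |
|---|---|---|---|
| Scan itself within ±3 days (Protocol 3.3.1) | 12–18 | 26–32 | 40–46 |
| Scan up to 3 days after a ±3-day visit (Protocol 3.1, SAP 2.1) | 12–21 | 26–35 | 40–49 |
| Scan up to 72 hours before ±3-day clinic procedures (Protocol 3.14.3.2) | 9–18 | 23–32 | 37–46 |
| All readings together | 9–21 | 23–35 | 37–49 |

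The combined windows do not overlap. SAP Table 1 gives days 14, 28 and 42. These agree with the protocol if they count days elapsed since infusion, because SAP 4.4 numbers the infusion day as day 1.

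**2. Where does a termination scan go?** Recorded as V7, it is week 6 under SAP 6.2.1.
- A scan on day 20 is 43 − 20 = 23 days before nominal week 6, and 37 − 20 = 17 days before the earliest day that any reading allows.
- A scan on day 29 is exactly at week 4, yet carries the week-6 label. It is 43 − 29 = 14 days early for week 6, and the week-4 value is left empty.

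**3. Does SAP 4.3 exclude later scans?** Its words stop at completion or withdrawal; Protocol 9.3 has no such stop; the SAP prevails. On that reading a scan obtained after withdrawal, as SAP 2.1 intends, is not used. On the other reading the explanatory clause makes the sentence a statement about imputation only. The text does not settle which is meant. A termination scan made at withdrawal passes either reading, so this point is separate from the label.

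**4. Scale (all inputs assumed).** If k of n patients in an arm are left out and differ from the rest by D percentage points, the arm mean moves by kD/n. With k = 1 and n = 6:
- D = 5: 5/6 = 0.8
- D = 10: 10/6 = 1.7
- D = 20: 20/6 = 3.3
- D = 30: 30/6 = 5.0

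One misplaced scan among six moves the week-6 mean by the same D/6.

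For a per-patient risk r of termination before the week-4 scan, the chance of at least one among 10 is 1 − (1 − r)^10: 9.6% for r = 1%, 40.1% for r = 5%, and 65.1% for r = 10%.

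As a rough guide to r, treat the 23% and 40% as risks at constant hazard over T weeks, so r = 1 − (1 − p)^(4/T). For T = 52 and T = 16 this gives 2.0% and 6.3% on reslizumab, and 3.9% and 12.0% on placebo. An asthma adverse event is not the same as an exacerbation that forces termination, so these only locate the range.

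**The case against.** **SAP 4.3 may only be a no-imputation statement.** Its explanatory clause says so, and Protocol 9.3 is built the same way. This stands as a fair alternative reading. A reader might infer that the SAP deliberately discards collected scans; the documents support only that it can be read so.

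**Few such scans may exist.** Protocol 4.4 and 3.14.4 provide for one final evaluation, and Protocol 6.1.1 counts 5 scans per patient. This also stands. A reader might infer that SAP 4.3 causes the week-4 loss, but most of it comes from mandatory termination under Protocol 3.12.

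**V7 has a ±3-day window, and week 6 is not primary.** The window governs scheduling. No analysis rule removes or reassigns a termination scan outside it, although misplacement is possible rather than prescribed. Week 4 is affected when the termination scan falls near day 29.

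**The analysis sets keep the patient.** A reader might take the replacement rule to make this a completers' analysis. It does not: the ITT set keeps every randomised patient, the FAS keeps those dosed with any post-baseline efficacy value, and earlier visits still count. Set membership without a week-4 value, however, adds nothing to the week-4 mean.

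**The study is exploratory, with no inferential statistics.** True, but a descriptive mean still needs defined inputs. A reader might also measure the shift against the plan's 5% signal window. That is an eligibility threshold comparing one patient with healthy controls, not a treatment-effect margin.

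**Conclusion.** The point holds in two parts of unequal strength. The firmer is the visit label: as written, an early-termination scan is eligible for the week-6 GLG and SUVmean summaries on any day, and one near day 29 is lost from the primary week-4 summary. The weaker is SAP 4.3: its plain words conflict with SAP 2.1 over scans after withdrawal, but another reading is available and few such scans may be made.

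Size and direction cannot be determined from the documents. Shifts of 0.8 to 1.7 percentage points follow from one patient in six and an assumed D of 5 to 10; a 5-point shift would need D = 30. A reader might infer a bias in favour of reslizumab. The documents do not support a direction: worsening could raise GLG, rescue steroids could lower it, and Protocol 1.1.2 names neutrophils as the main source of lung FDG signal.

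**What to change.** Amend the SAP before database lock.

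1. **Assign early-termination PET/CT scans by actual study day.** State one window per week that covers both the scan-before and scan-after readings, for example days 9–21, 23–35 and 37–49, with infusion as day 1. Leave scheduled V5, V6 and V7 scans at their nominal week. Where a scheduled scan exists for that week, use it; otherwise the last-non-missing rule in SAP 4.4 would let the termination scan replace it. List an out-of-window scan with its study day and do not count it as week 6.
2. **State which scans count.** Summarise GLG and SUVmean from all collected post-dose scans of randomised patients regardless of withdrawal. Add a second prespecified summary excluding scans after withdrawal or systemic steroids.

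No extra disposition table is needed: SAP 5.2 already covers withdrawals with reasons, and SAP 8.2 plans a summary of asthma deterioration.

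The cost is a SAP amendment and one extra set of summaries. It governs only scans that are collected. It should not be read as asking for a termination scan plus every scheduled scan, which would be 2 + 3 + 1 = 6 scans and 6 × 800 = 4800 mrem, against the 5 scans and 4000 mrem in Protocol 6.1.1. The downsides are that some post-rescue scans enter one of the two summaries, and that patients with no scan near week 4 remain missing.
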